The second visit will begin with the first rTMS session (also described below) which will then be followed directly by the post-rTMS MRI scan. Starting the following day, the subsequent nine sessions will consist only of rTMS for a total of 10 rTMS sessions. The sessions in the rTMS series will take place daily across two weeks excluding weekends. A post-testing session, scheduled the week after the final rTMS session, will include an MRI scan and repeat administration of the language assessments that were administered during the screening visit. A final follow-up session, identical in design to the post-testing session, will be scheduled in an additional 7-10 weeks. All study-related evaluations will be administered by the PI (a licensed speech-language pathologist) or in Year 2 by the staff speech-language pathologist. Study participants will receive up to \$275 for time and local travel expenses and up to an additional \$1500 to defray lodging expenses incurred as part of study participation, to be pro-rated if they do not complete all study procedures (including follow-up visits).

Participants will be pseudo-randomly assigned to an rTMS treatment group (priming stimulation vs no priming stimulation) depending on the outcome of their baseline fMRI (described in C1.1, below). That is, an equal number of participants with and without baseline RH PTr activation will be approximated in each group.

C.1.1 MRI Procedure

fMRI Overt Confrontation Picture Naming Task. Images will be acquired using a 3.0 Tesla parallel-acquisition, echo-planar equipped Siemens MRI scanner. Participants will lay supine in the scanner wearing hearing protection and over-ear headphones. Their heads will be secured with foam padding to minimize movement.

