Motor Threshold and Intensity Determination. To standardize TMS stimulation intensity prior to rTMS, a resting motor evoked threshold (MT) will be established based on a distal upper extremity motor response. The MT will be measured by delivering single stimulations to the motor cortex with gradually increasing intensity no more frequently than every 3 sec, i.e. ~0.3 Hertz. Threshold is defined as the lowest intensity of stimulation producing motor evoked potentials of at least 50 μ V (or a visible movement of the digit) in 5 of 10 trials. Our standard stimulation intensity will be 90% of the MT.

Individual fMRI-based coil targeting. Evidence suggests that the degree of spatial resolution required to target specific cortical sites such as the PTr is achieved more readily when rTMS is used in conjunction with image-guided navigation techniques [48]. This stereotactic targeting also ensures more consistent coil placement across sessions. Following individual determination of stimulation intensity, coil placement individually targeted to the RH PTr will be performed using a frameless stereotactic method as described in Neggers and colleagues [49] and will be implemented in the BrainVoyagerQX software neuro-navigation package. Following coil positioning, participants will receive rTMS treatment according to their group assignment (see below).

TMS Administration.

Group A: Inhibitory only rTMS group: Inhibitory 1Hz rTMS will be applied continuously for 1200 pulses (20 minutes) 5 days per week across 2 weeks (10 sessions total).

Group B: Excitatory primed rTMS group: The inhibitory sequence described above will be preceded for each session by priming stimulation which will consist of intermittent 6-Hz rTMS applied in 5 second trains with 25 second intervals between trains for a total 600 pulses (10 minutes).

C2. Data Analysis

C2.1 Analysis of Behavioral Measures: Naming data (item-level performance on the PNT) will be used for analysis of rTMS treatment effects by group. Accuracy data will be analyzed using multilevel linear or logistic regression in R. Models will include fixed effects of session (baseline, post-treatment, follow-up), and group (Group A, Group B) and random effects of subject and item. Analyses may include additional random-effects structure if needed to improve model fit.

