C2.2 fMRI Processing/Data Analysis: All processing will be performed using SPM12 (The Wellcome Trust Centre for NeuroImaging, UCL, UK). The concatenated functional image sequences (runs) will be preprocessed with standard fMRI analysis routines that include slice time acquisition correction, realignment,

registration to structural images, spatial normalization, and spatial smoothing. The data will also be filtered for low frequency scanner drift.

Within-subject data (first level) will be analyzed using a general linear model with a finite impulse response (FIR) basis function to model the individual HRF. For each participant, we will generate an individualized map of brain activity for the contrast of naming > baseline (crosshair fixation) including factor of MRI session for both correct and incorrect responses. Movement parameters will be entered as regressors of no interest to control for participant head movement in the scanner. Activation maps for all contrasts will be thresholded to $p=0.05$ (cluster corrected using Family-Wise Error (FWE)). Resulting contrast values (effect sizes) for each contrast will be entered into a second level/random effect analysis by group (Group A: inhibitory only rTMS vs Group B: excitatory primed inhibitory rTMS). Region of Interest (ROI) analysis will be performed to estimate activation for RH PTr for all described contrasts using the MarsBaR toolbox for SPM.

To assess the relative contribution of the right versus left hemisphere (hemispheric lateralization) to the fMRI naming task, whole brain laterality indices (LI) will be calculated for each scan using the LI-toolbox for SPM [50]. As LI calculation relies on the computation $LI = (Left-Right) / (Left+Right)$, a negative value indicates a right hemispheric dominance and a positive value indicates a left hemispheric dominance. LI values will be generated using t-maps from the first level analyses described above.

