Dynamic causal modeling (DCM) will be used to estimate effective connectivity changes due to inhibitory rTMS across time. Regions to be included in the DCM analysis will be derived from clusters of contiguous voxels surviving an omnibus F-test for the effect of interest (correct naming > crosshair fixation) at $p < 0.001$ uncorrected from the first-level fMRI analysis. Regions will be constrained to only include those clusters that fall within the traditionally outlined “language network” in the LH (inferior frontal lobe, temporal lobe, and portions of the inferior and posterior parietal lobe, [51]) and the corresponding RH homologues. The effective connectivity model (estimate of coupling and weights between these regions) will be estimated via post-hoc network discovery methods [52]. This method uses Bayesian model selection methods to select the model that was the most likely to have generated the time series data from all possible combinations of bi-directional connections between the regions. Coupling weights for interhemispheric connections will be summed for each participant for each scanning session. Other post-hoc analyses of the DCM results may be undertaken to explore both inter- and intra-hemispheric network level effects of the rTMS.

Finally, change in naming accuracy on the PNT across sessions will be correlated with change in LI, functional activation in RH PTr, and interhemispheric effective connectivity across sessions. A positive correlation between naming gains and 1) a left-hemisphere directed LI shift, and 2) a decrease in RH inhibition of LH (more positive RH to LH directional coupling weights) will support Hypothesis 1a and 1b, respectively. A positive correlation between the magnitude of pre-TMS RH PTr activation and 1) decrease in RH PTr activation across scan sessions, and 2) magnitude of left-hemisphere directed LI shift will support Hypothesis 2a and 2b, respectively. A significant interaction of group and session (analysis C2.1) suggesting that Group B receiving the 6 Hz primed inhibitory rTMS showed greater naming improvement across time will support Hypothesis 3.

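### C2.2 chooses connectivity-model regions by each participant's own activation, so RH PTr, the stimulated region, can be missing from some of the models behind the Hypothesis 1b correlation

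*Combined protocol and SAP*

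**What the plan says.** **Who is enrolled and stimulated.** C.1 Procedures assigns participants to a group "depending on the outcome of their baseline fMRI", so that "an equal number of participants with and without baseline RH PTr activation will be approximated in each group". Participants with no baseline activity in RH PTr are therefore expected by design. C 1.2 stimulates the same site in everyone: "coil placement individually targeted to the RH PTr will be performed using a frameless stereotactic method". No exception is made for activation status.

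**How model regions are chosen.** C2.2 states: "Regions to be included in the DCM analysis will be derived from clusters of contiguous voxels surviving an omnibus F-test". The contrast is correct naming against fixation, and the threshold is p<0.001 "uncorrected from the first-level fMRI analysis". First level means within participant: "Within-subject data (first level) will be analyzed using a general linear model with a finite impulse response (FIR) basis function". The further limit to the LH language network and its RH counterparts filters the surviving clusters. It does not add a region that failed to survive.

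**What is done with the model.** The weights on between-hemisphere connections are added up per participant and scan, and their change is correlated with change in PNT accuracy. For Hypothesis 1b the supporting result is a positive correlation of naming gain with "a decrease in RH inhibition of LH (more positive RH to LH directional coupling weights) will support Hypothesis 1a and 1b, respectively".

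**Where RH PTr is fixed.** The separate activation analysis in C2.2 does fix RH PTr as a MarsBaR region of interest for all contrasts. The DCM paragraph does not carry that over.

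**The concern.** Sections A1 to A3 give the inhibitory influence of the right hemisphere, and of RH PTr in particular, as the reason for stimulating this site. A3.2 says that no study has directly tested whether rTMS changes directional influence between the hemispheres. Hypothesis 1b is the plan's test of that idea. A model without an RH PTr node cannot show any change in the influence of the stimulated region.

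Under the selection rule the node can be absent for some participants, and the plan itself expects people in whom the region is not recruited. Their summed coupling is still a number, and it goes into the same correlation as sums that do include RH PTr. One variable then has two meanings, and which meaning applies to a participant is related to the assignment factor. A weak or strong correlation could reflect which regions happened to be modelled rather than the mechanism under study.

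**Working it through.** The plan states no figure to reproduce on this point. The check has three parts.

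**1. What losing the node does to the sum.** With kL left and kR right nodes, the possible directed interhemispheric connections number 2 × kL × kR, of which kL × kR run from RH to LH. Removing RH PTr replaces kR by kR − 1. The documents give no node counts, so these are assumed:

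| LH nodes, RH nodes | All interhemispheric, with → without RH PTr | RH to LH, with → without |
|---|---|---|
| 2, 2 | 8 → 4 | 4 → 2 |
| 3, 3 | 18 → 12 | 9 → 6 |
| 4, 4 | 32 → 24 | 16 → 12 |
| 3, 1 | 6 → 0 | 3 → 0 |

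These are maxima, because the network search may retain fewer connections. Take the 3, 3 case. If every RH-to-LH weight rose by the same amount d, the sum would rise by 9d with RH PTr in the model and by 6d without it. If only the three weights leaving RH PTr rose, the sum would rise by 3d with the node and by 0 without it. Equal biology gives unequal values.

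**2. Is the node certain to be absent when RH PTr is inactive at baseline?** No. The stratum rule and the DCM rule differ in three ways.
- Scan: the stratum rests on baseline alone. The first-level model is described as "including factor of MRI session for both correct and incorrect responses", four scans are planned (baseline, after the first rTMS session, post-testing, follow-up), and the F-test is not limited to baseline.
- Threshold: C.1 names none for activation. C2.2 uses cluster-level FWE at 0.05 for its maps but p<0.001 uncorrected for DCM regions.
- Sign: an omnibus F-test has none, so a deactivation or a later change can also survive.

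As an illustration, assume one effect per session, four sessions, F on 4 and 500 degrees of freedom, p<0.001, and noncentrality = (baseline z)² + 3 × (later z)². The FIR model would have more parameters, so this is a simplification.

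| Baseline z | Later z | Noncentrality | Chance RH PTr survives |
|---|---|---|---|
| 0 | 0 | 0 | 0.001 |
| 0 | 2 | 12 | 0.32 |
| 0 | 3 | 27 | 0.88 |
| 4 | 0 | 16 | 0.51 |
| 4 | 3 | 43 | 0.99 |

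Two things follow. A participant inactive at baseline may or may not have the node. And if all sessions enter the test, whether the node is present depends on what RH PTr does after rTMS, so the node is partly selected on response to treatment. A.3.1 notes that 1 Hz stimulation can be excitatory in an already inhibited region, so such a change is plausible.

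**3. How many participants.** Planned enrollment is 6 + 10 = 16 (Study timeline). If the strata were split evenly, 16 / 2 = 8 would be inactive at baseline, and all 8 would lack the node only if none passed the F-test. The documents give neither the split nor the pass rate.

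**The case against.** The strongest reply is that Hypothesis 1b is worded by hemisphere, not for RH PTr. A participant without that node still contributes through any surviving right temporal, parietal or other frontal region, so the hypothesis remains computable. A.3.1 also says that people who keep LH PTr function would recruit RH PTr little, so an absent node in them fits the study's own account. The response at the stimulated site is still captured by the fixed ROI, and forcing a weakly responding region into a task-based DCM produces poorly determined weights.

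Most of this stands, and it limits the point. Three stronger readings are tempting but not supported:
- A reader might infer that RH PTr drops out for the whole inactive stratum. The two criteria differ in scan, threshold and sign, so this is possible for each participant but not a rule.
- A reader might infer that the node vanishes in the scans where rTMS worked best. That needs regions to be chosen scan by scan. C2.2 does not say so; what it does per scan is add up the weights.
- A reader might infer that Hypothesis 1b is tested only in the active half, with precision to match. The plan excludes no one for lacking the node, so an interval at a reduced sample size would describe an analysis that it does not contain.

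The reply does not remove the core. The correlation still mixes sums with and without the stimulated region, and no visible text says how that is handled. The fixed ROI measures activation, which is a different quantity from coupling.

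**Conclusion.** The concern holds in a limited form. The DCM selection rule does not guarantee that the stimulated region is a node. RH PTr can be absent from some participants' models and will be where no RH PTr cluster survives. The planned sum is then not comparable between participants: with three nodes per hemisphere the possible RH-to-LH connections fall from 9 to 6, and with two from 4 to 2. If all sessions enter the F-test, inclusion can also depend on the post-rTMS response.

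The node counts are assumptions. The number of participants affected is unknown; about 8 of 16 is an upper illustration that needs both an even split and failure of the F-test by every inactive participant. Some text between the Preliminary Studies heading and C.1 was not available to this review, so a definition of activation or a fuller statement of Hypothesis 1b there cannot be excluded. The matter should be corrected before the connectivity analysis. It does not invalidate that analysis or touch the behavioral one.

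**What to change.** In C2.2:
- State that RH PTr is a node in every participant's DCM, with its time series taken from the anatomical ROI already planned in MarsBaR, whether or not the F-test is passed.
- Use the F-test only to add further regions. Say which sessions enter it, and hold each participant's node set constant across all scans.
- Report RH PTr-to-LH coupling for Hypothesis 1b alongside the planned sum, and show it by baseline activation stratum. This requires C.1 to define baseline RH PTr activation by contrast and threshold.

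The cost is analysis wording only, with no new data or scans. Coupling estimates will be less precise where RH PTr is weakly active; showing results by stratum makes that visible. The remaining nodes will still differ between participants, so the number of connections behind each reported value should be given.

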Researchers in the stroke motor-recovery literature have controlled for the potential paradoxical effect of 1 Hz rTMS by first administering a 6 Hz rTMS pulse sequence. In contrast to slow rTMS, pulse sequences above 5 Hz have an excitatory effect [37]. This excitatory pulse sequence in essence “primes” the targeted brain region so that the 1Hz pulse sequence has the expected inhibitory effect, while at the same time enhancing the effect [38]. To date, only one study has applied an excitatory priming sequence to control for potential varying levels of cortical excitability in aphasia. In this study by Kakuda and colleagues [39], participants received 10 minutes of 6 Hz priming stimulation prior to 20 minutes of 1 Hz low-frequency rTMS to RH PTR every weekday for two consecutive weeks. The rTMS was followed by 60 minutes of speech-language therapy (SLT). Improvement was noted for all four participants on both receptive and expressive language measures following the series of rTMS sessions. However, this study had several critical limitations, most notably that all participants received speech-language therapy as part of the protocol. It is therefore impossible to determine the source of the measured improvements (the rTMS, the SLT, or their interaction). In addition, as all participants received the excitatory priming sequence, the study was unable to conclude whether the excitatory priming produced any additional benefit above and beyond that of the standard 1Hz rTMS protocol.

It is highly likely that pre-rTMS RH PTR excitability *would* differ between individuals with chronic aphasia depending on the extent to which it is recruited during recovery. If an individual with chronic aphasia retained some function of LH PTR, which would be expected for those individuals without left frontal lesions, they would not be expected to demonstrate a large amount of compensatory recruitment of RH PTR [28], and hence show little benefit from rTMS induced inhibition of this area. In fact, Kakuda and colleagues in a different study [40] found that the location of peak activation during functional magnetic resonance imaging (fMRI) of a repetition task was in the left hemisphere perilesional areas for over half of the participants with chronic aphasia in their study. *Therefore, it is imperative to have pre-rTMS neuroimaging measures of levels of RH PTR activation in order to accurately interpret the rTMS effects.*

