A.3.2 Extent of left-hemisphere focused shift in activation

There is little direct neuroimaging evidence to support the hypothesis that inhibitory rTMS to RH PTR promotes recruitment of intact LH perilesional cortical areas. Several of the rTMS studies in aphasia that measured functional activation did so only *prior* to rTMS and did not investigate pre-post rTMS changes [40-41]. To date there have been only two studies that have investigated differences in task-related regional brain activation *before* and *after* inhibitory rTMS to RH PTR in order to test this hypothesis. Martin and colleagues [34] found that, for one participant, a LH shift in activation post-rTMS corresponded to improved naming, whereas for the other participant, for whom no naming improvement was seen, no such activation shift was noted. Despite offering support for the inhibition hypothesis, this study has several significant limitations. First, the authors used a blocked functional magnetic resonance imaging (fMRI) design to measure naming-related brain activation. Although the block design offers more power to detect small effects, neural responses to individual trials within a block cannot be evaluated separately. This is especially important when evaluating lateralization of activation during naming as other studies have noted differences in lateralization for correct compared to incorrect naming responses in chronic aphasia [26]. Secondly, post-rTMS fMRI scans were only performed beginning at 3 months after rTMS conclusion. Because of this delay, it is unclear whether the

observed activation changes are a cumulative result of the multiple rTMS sessions (via the LTD-like effect), experience-dependent reinforcement of the newly recruited areas within the LH language network, or both. Finally, the study included only 2 participants, limiting the statistical power and analyses that could be performed as well as the generalizability of the findings to a broader group of individuals with chronic aphasia.

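### The H1 and H2 correlations leave out left frontal damage, which the protocol itself expects to influence RH PTr recruitment and benefit, so they can be biased in either direction

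*Combined protocol and SAP*

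**What the plan says.** The closing paragraph of C2.2 sets out the tests: "change in naming accuracy on the PNT across sessions will be correlated with change in LI, functional activation in RH PTr, and interhemispheric effective connectivity". H1a rests on "A positive correlation between naming gains and 1) a left-hemisphere directed LI shift", and H1b on the matching correlation with RH-to-LH coupling. H2a and H2b take baseline RH PTr activation as the predictor; the second is judged by the "magnitude of left-hemisphere directed LI shift will support Hypothesis 2a and 2b, respectively". No covariate, alpha level or sidedness is given for any of the four. Only H3 is described in terms of significance.

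No lesion term appears elsewhere in the analysis. The C2.1 model has session and group as fixed effects, and subject and item as random effects. The only nuisance regressors named in C2.2 are head-movement parameters. Structural images are in hand, since preprocessing includes "registration to structural images, spatial normalization, and spatial smoothing".

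The background gives lesion site a role. On people who keep some LH PTr function, section A.3.1 says: "which would be expected for those individuals without left frontal lesions, they would not be expected to demonstrate a large amount of compensatory recruitment". The region meant is RH PTr, and the protocol concludes that such people would "hence show little benefit from rTMS induced inhibition of this area". Section A.3.2 states the hypothesis under test as being that rTMS "promotes recruitment of intact LH perilesional cortical areas".

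**The concern.** On the protocol's own account, left frontal damage comes before baseline RH PTr activation and before benefit. If the leftward shift goes into intact left cortex, damage there may also affect how far activation can move. These are the quantities that C2.2 correlates. A factor that affects both members of a pair produces a correlation between them without any direct link, or cancels one that exists.

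Two features of the design might seem to deal with this, but they do not. Balancing the groups on baseline RH PTr activation (C.1) helps the Group A versus Group B comparison in H3, not correlations taken across all participants. Change scores remove a constant lesion effect on level, but not a lesion effect on the amount of change.

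At stake is the mechanistic conclusion of the study: whether naming gain tracks the hemispheric shift, or whether both reflect where the stroke was.

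**Working it through.** The available text has no power or effect-size calculation to reproduce.

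**Inputs**
- n = 6 + 10 = 16 (Study timeline).
- Two-sided alpha of 0.05: assumed, because C2.2 states none for these tests.
- a and b, the correlations of left frontal damage with the two variables in a pair: not in the documents, so assumed at 0.3, 0.5 and 0.7 in size, with either sign.

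**Formula.** With ρ the partial correlation given lesion, the expected unadjusted correlation is r = ab + ρ·√[(1 − a²)(1 − b²)]. With no true link (ρ = 0) this reduces to r = ab. Frequencies come from 100,000 simulated trials of n = 16 per scenario.

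**No true link (ρ = 0)**

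| Size of a and b | Signs | Expected r | r > 0 | r > 0 and p < 0.05 |
|---|---|---|---|---|
| 0 | none | 0 | 50% | 2.5% |
| 0.3 | same | +0.09 | 63% | 5% |
| 0.5 | same | +0.25 | 83% | 15% |
| 0.7 | same | +0.49 | 98% | 51% |
| 0.3 | opposite | -0.09 | 37% | 1.1% |
| 0.5 | opposite | -0.25 | 17% | 0.2% |
| 0.7 | opposite | -0.49 | 2% | under 0.1% |

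The partial correlation returns about 50% and 2.5% in every row. The r > 0 column matters because C2.2, read literally, asks only for a positive correlation.

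**H2b with a true partial r of 0.5.** Suppose damage raises RH PTr activation and limits the leftward shift. Then r = −0.09 + 0.5 × 0.91 = 0.365 at 0.3, −0.25 + 0.5 × 0.75 = 0.125 at 0.5, and −0.49 + 0.5 × 0.51 = −0.235 at 0.7. Power falls from 53% to 29%, 7% and 0.3%; the adjusted test stays at about 50%. If damage instead raises both variables, H2b is inflated as in the same-sign rows.

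**Which sign do the documents imply?**
- A.3.1: no left frontal lesion, little benefit. So damage and gain are positively related.
- A1: left frontal recruitment predicts naming gain. So loss of that tissue could lower gain.
- A.3.2: the shift is into intact left cortex. One may infer that damage limits the shift, but no lesion effect on LI is stated.

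The A.3.1 and A.3.2 readings together give opposite signs and make H1a harder to support. The A1 and A.3.2 readings together give the same sign and inflate it. The direction is open.

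**Cost of adjusting.** Critical r = t/√(t² + df). With no covariate, df = 14 and r = 0.497. With one, df = 13 and r = 0.514. With three (lesion, baseline PNT, baseline LI), df = 11 and r = 0.553. If lesion has no effect, power with one covariate falls from 53% to 50% at a true r of 0.5, and from 73.5% to 70% at 0.6.

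**The case against.** A reader might infer that smaller lesions bring both more naming gain and more leftward shift, so that H1a would be falsely supported while H2b is hidden. The documents do not support that as a fixed direction. Hiding H2b requires damage to raise RH PTr activation and reduce the shift. For H1a to be inflated as well, damage would also have to reduce naming gain, which runs against A.3.1. If damage raises gain and shift together, H1a and H2b are both inflated and nothing is hidden.

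A reader might also infer that total lesion extent determines recruitment. A.3.1 speaks of what is expected, and names left frontal site and residual LH PTr function rather than overall volume.

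Three further objections have weight. If damage affects naming only through the LI shift, that is the mechanism in H1a and not confounding. For H2, baseline RH PTr activation is downstream of the lesion, so adjustment removes variation that the hypothesis is meant to use and changes the question. For H1b, no passage links lesion to change in coupling, so its exposure to bias is an assumption. It is also fair to say that measuring RH PTr activation directly, as the plan does, is a reasonable choice in a study of this size.

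These points limit the adjustment and argue for showing both estimates. They do not make the unadjusted correlation alone sufficient: the direction of bias is unknown, and nothing in C2 would reveal it.

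**Conclusion.** The point stands as an omitted pre-treatment factor whose effect can go either way. It does not show that H1a will be falsely supported or that H2b will be lost. With no true link, the chance of meeting the positive-correlation rule runs from 2% to 98%, instead of 50%, over the assumed lesion correlations.

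This rests on assumed correlations of 0.3 to 0.7, on linear relations and on n = 16. The return to 50% and 2.5% holds only if the chosen measure captures the confounder without appreciable error. The text between the Preliminary Studies heading and the methodological remarks before C.1 was not available. An eligibility limit on lesion there would narrow the variation and shrink these figures, but it would not put a lesion term into C2.

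**What to change.** - Before outcomes are viewed, outline the lesion on the baseline structural scan and record the percent of left inferior frontal gyrus, including PTr, that is damaged.
- Report H1a and H1b as partial correlations adjusted for that single measure, beside the unadjusted r. Call H1 supported only if the adjusted estimate agrees in direction.
- For H2a and H2b, keep the unadjusted correlation as the test and report the lesion-adjusted one as a sensitivity analysis.
- Use total lesion volume only as a sensitivity covariate. Do not add baseline PNT and baseline LI to the lesion term: 11 degrees of freedom would remain.

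The cost is sixteen lesion outlines, with no additional scan, and a short addition to C2.2. Statistically it is one degree of freedom: critical r goes from 0.497 to 0.514, about 3 points of power.
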